2. STUDY OBJECTIVES AND ENDPOINTS

2.1 Study Objectives

2.1.1 Primary Objective

- To compare the safety of UCMSCs and BMMSCs administered intravenously in patients with chronic inflammation due to metabolic syndrome.

2.1.2 Secondary Objectives

- To demonstrate the efficacy of UCMSCs and BMMSCs administered intravenously in patients with chronic inflammation due to Metabolic Syndrome as assessed by (see Table 9 in Section 2.2.2):

- symptom related quality of life
- cardiovascular status
- inflammatory cytokines
- endothelial function
- lipid profile
- glucose homeostasis
- 1 year survival

2.2 Study Endpoints

2.2.1 Primary Endpoints (Safety)

Safety will be assessed as the incidence within one month after an infusion of any treatment emergent serious adverse events (TE-SAEs), defined as one or more of the following events that: is life-threatening event (e.g., stroke or non-fatal pulmonary embolism); requires inpatient hospitalization or prolongation of existing hospitalization (e.g., for worsening dyspnea); results in persistent or significant disability/incapacity; results in death; or leads to clinically significant untoward laboratory test result(s) or medical condition(s), determined per Investigator' judgments.

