3. STUDY DESIGN

3.1 Description of the Study

A Pilot Phase will be performed to test the safety of dose and volume of cells administered via peripheral intravenous infusion. The first three (3) subjects in-group 1 (UCMSCs) will be treated first and safety will be fully assessed. Only if there is no evidence of treatment emergent SAEs in Group 1, treatment of subjects in Group 3 be undertaken.

The subjects in the high dose (Groups 3 & 4) will not be treated until the subjects in the low dose (Groups 1 & 2) have completed their one-month follow-up assessments and safety measures have been reviewed to confirm that there have been no treatment emergent SAE's. Treatment emergent SAE's, defined as the composite of: death, non-fatal pulmonary embolism, stroke, hospitalization for worsening dyspnea and clinically significant laboratory test abnormalities, prior to proceeding with the treatment of further subjects.

Subjects in each pilot phase group (Group 1, 2, 3 and 4) will not be treated less than 5 days apart.

Subjects in the pilot phase will receive a telephone call 5 days post infusion (+/- 1 day) to review adverse events.

The randomized portion of the study will be conducted after a full review of the safety data from the Pilot Phase by the DSMB.

Following the pilot study (12 subjects), thirty (30) subjects that meet inclusion criteria will be scheduled to undergo peripheral intravenous infusion.

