8.1.1 Laboratory Evaluations

At screening, the HIV-1 and HIV-2 tests, Syphilis – VDRL (If VDRL is reactive Confirmation with FTA-ABS is needed), CMV, hepatitis screen and β -HCG serum pregnancy tests (only for women of childbearing potential) will be performed locally at the study site. Laboratory safety tests will consist of the following:

Serum chemistry: sodium, potassium, chloride, BUN, creatinine, glucose, calcium, AST/SGOT, ALT/SGPT, carbon dioxide, total bilirubin (fractionate if total >1.5 times normal), alkaline phosphatase, albumin, fibrinogen, IL6, D-Dimer, Coagulation studies

Hematology: hemoglobin, hematocrit, platelets, WBC, RBC,

The Investigator will review all clinically relevant laboratory results requested in the protocol. The diagnosis associated with any clinically significant laboratory deviations should be recorded as an AE and should indicate the underlying abnormality or diagnosis (such as renal insufficiency) as opposed to the observed deviation in laboratory results (such as elevated creatinine). If there is no underlying abnormality linked to a clinically significant abnormal laboratory value, the observed deviation should be reported as the AE.

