8.5 Definition of Serious

An adverse event (AE) or suspected adverse reaction is considered "serious" if it:

1. results in death
2. is life-threatening (at risk of death at the time of the event)
3. requires in inpatient hospitalization or prolongation of existing hospitalization

NOTE: Complications that occur during hospitalization are AEs. If a complication prolongs hospitalization or fulfills any other serious criteria, the event is serious.

Hospitalization for elective treatment of a pre-existing condition that did not worsen from baseline is not considered to be an AE.

4. results in disability/incapacity

*NOTE: The term **disability** means a substantial disruption of a person's ability to conduct normal life functions. This definition is not intended to include experiences of relatively minor medical significance such as uncomplicated headache, nausea, vomiting, diarrhea, influenza, accidental trauma (i.e., sprained ankle) that may interfere or prevent everyday life functions but do not constitute a substantial disruption.*

5. is a congenital anomaly/birth defect.

Important medical events that may not result in death, be life-threatening, or require hospitalization may be considered an SAE when, based upon appropriate medical judgment, they may jeopardize the subject and may require medical or surgical intervention to prevent one of the outcomes listed in the above definition.

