8.6 Definition of Unexpected

An adverse event or suspected adverse reaction is considered “unexpected” if it is not listed in the investigator brochure or is not listed at the specificity or severity that has been observed; or, if an investigator brochure is not required or available, is not consistent with the risk information described in the general investigational plan or elsewhere in the current application.

8.7 Clinical Laboratory Assessments and Other Abnormal Assessments as Adverse Events and Serious Adverse Events

Abnormal laboratory findings (e.g. clinical chemistry, hematology) or other abnormal assessments (e.g., vital signs) that are judged by the Investigator as clinically significant will be recorded as AEs or SAEs if they meet the definition of an AE as defined in Section 8.3 (“Definition of an Adverse Event”) or SAE, as defined in Section 8.6 (“Definition of a Serious Adverse Event”). Clinically significant abnormal laboratory findings or other abnormal assessments that are detected during the study or are present at screening and significantly worsen following the start of the study will be reported as AEs or SAEs. However, clinically significant abnormal laboratory findings or other abnormal assessments that are associated with the disease being studied, unless judged by the Investigator as more severe than expected for the subject's condition, or that are present or detected at the start of the study but do not worsen, will not be reported as AEs or SAEs.

The Investigator will exercise medical judgment in deciding whether abnormal laboratory values are clinically significant.

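### The primary endpoint is labelled an SAE incidence, but its last limb has no seriousness threshold, so it counts events that are not serious under 8.5 and that 8.7 may leave unrecorded

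*Combined protocol and SAP*

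**What the plan says.** Section 2.2.1 defines the primary safety endpoint as the incidence of TE-SAEs within one month of infusion. It lists five alternative limbs: a life-threatening event, hospitalization or its prolongation, persistent or significant disability, death, and an event that "leads to clinically significant untoward laboratory test result(s) or medical condition(s), determined per Investigator' judgments".

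Four other places bear on the same events:

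- Section 8.5 defines serious by outcome. For events outside the listed outcomes it has an important-medical-event clause: such events "may be considered an SAE when, based upon appropriate medical judgment, they may jeopardize the subject and may require medical or surgical intervention", where that intervention would avert a listed outcome.
- Section 8.7 sends clinically significant findings to AE or SAE according to the general definitions. It then exempts "clinically significant abnormal laboratory findings or other abnormal assessments that are associated with the disease being studied", unless the investigator judges them worse than expected for that subject. Section 8.2 has a parallel exclusion for expected progression of the disease under study.
- Section 8.1.1 covers coding: record the diagnosis rather than the laboratory value. Where there is none, "If there is no underlying abnormality linked to a clinically significant abnormal laboratory value, the observed deviation should be reported as the AE".
- Section 3.1 gives a different TE-SAE composite for the pilot gate: death, non-fatal pulmonary embolism, stroke, "hospitalization for worsening dyspnea and clinically significant laboratory test abnormalities".

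Section 8.1.5 item 9 has the DSMB monitor the 30-day proportion using the 2.2.1 definition. Section 9.2 does not say how the TE-SAE count is derived.

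**The concern.** The primary objective (2.1.1) is to compare the safety of the two cell products. A reader of the results will take an incidence of serious adverse events to mean what 8.5 says serious means. Under 2.2.1, one asymptomatic laboratory value that an investigator calls clinically significant carries the same weight as a death.

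Completeness is a second problem. If a last-limb event may lawfully go unrecorded under 8.7 or 8.2, the primary endpoint cannot be fully reconstructed from the AE data. The population makes this more than theoretical. Section 4.1 requires three of five metabolic criteria, and only waist circumference and blood pressure are not laboratory measures. Every subject therefore qualifies on at least one of triglycerides, HDL or glucose, by value or by drug treatment. Table 12 schedules the metabolic and lipid panels at Week 2 and Month 1, so these values are looked at in or close to the primary window.

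**Working it through.** The plan states no expected TE-SAE rate, power or margin, and 9.1 says that no formal sample-size justification was made. There is no plan figure to reproduce, so the check is mainly a comparison of the texts.

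**How each definition treats a finding within one month of infusion**

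| Finding | 2.2.1 | 3.1 | 8.5 | 8.7 and 8.2 |
|---|---|---|---|---|
| Laboratory event that meets 8.5 | counts | counts | serious | recorded as SAE |
| Significant laboratory finding below 8.5, not disease-associated | counts | counts | not serious | recorded as AE |
| Significant laboratory finding below 8.5, disease-associated, judged no worse than expected | counts | counts | not serious | may go unrecorded |
| Significant non-laboratory condition below 8.5 | counts | not listed | not serious | AE, with the same conditional exclusion |
| Hospitalization for a reason other than dyspnea | counts | not listed | serious | recorded as SAE |

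Row 1 shows the overlap. Rows 2 to 4 show where 2.2.1 and 8.5 part. Row 3 shows where an event can belong to the endpoint and yet be absent from the data. Rows 4 and 5 show that 3.1 is a different set from both 2.2.1 and 8.5.

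**Illustration of size (both rates are assumptions, not document figures)**

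Let s be the one-month risk of an event meeting 8.5, taken as 2% to 5%. Let l be the risk of a significant finding below 8.5, taken as 10% to 30%. Assuming independence, the 2.2.1 risk is p = 1 − (1 − s)(1 − l). With 10 subjects per randomized arm (synopsis), the expected number with an event is 10p, and the chance of at least one is 1 − (1 − p)^10.

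| s | l | p | Expected of 10 | Chance of at least one | Ratio to 8.5 only |
|---|---|---|---|---|---|
| 2% | none (8.5 only) | 0.020 | 0.20 | 18% | 1 |
| 2% | 10% | 1 − 0.98 × 0.90 = 0.118 | 1.18 | 72% | 1.18/0.20 = 5.9 |
| 2% | 30% | 1 − 0.98 × 0.70 = 0.314 | 3.14 | 98% | 3.14/0.20 = 15.7 |
| 5% | none (8.5 only) | 0.050 | 0.50 | 40% | 1 |
| 5% | 10% | 1 − 0.95 × 0.90 = 0.145 | 1.45 | 79% | 1.45/0.50 = 2.9 |
| 5% | 30% | 1 − 0.95 × 0.70 = 0.335 | 3.35 | 98% | 3.35/0.50 = 6.7 |

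Over this grid the 2.2.1 count is about 3 to 16 times the 8.5 count. For example, the same arm could read 0/10 under 8.5 (exact 95% interval 0 to 31%) and 3/10 under 2.2.1 (7% to 65%). The ratio depends on the assumed rates and tends to 1 as l approaches zero.

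**The case against.** The other side has several fair points.

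- A reader might infer that 8.1.1, 8.5 and 8.7 class all these findings as ordinary AEs. They do not. Section 8.1.1 is a coding rule and every SAE is also an AE, 8.7 allows for either, and the important-medical-event clause in 8.5 can make a laboratory event serious.
- A reader might infer that a glucose rise after infusion is simply unreportable. That is also too strong. Section 8.7 requires reporting of findings that significantly worsen after the start of the study, and 8.2 lists significant or unexpected worsening of the condition under study as an AE. The exemption depends on a judgement that the finding is disease-associated and no worse than expected.
- A reader might infer that the trial will count the endpoint from the 8.5 seriousness field. Nothing in the documents says so. The one place that ties the monitored proportion to a definition, 8.1.5 item 9, names 2.2.1.
- A sponsor may choose a broad safety composite in a small early-phase trial. The DSMB closed report lists adverse events and serious adverse events separately (9.4.3.3), and 8.1.5 and 9.3 say that the guidelines are not formal stopping rules. A serious signal is therefore not hidden from the DSMB.
- In the randomized phase investigators are to be blinded (6.6), so incomplete recording need not favour an arm.

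These points narrow the concern but do not remove it. The composite is still called an SAE incidence, its last limb still lacks the threshold in 8.5, and row 3 of the first table still describes a primary event that need not be recorded.

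**Conclusion.** The point holds as a contradiction within the definition of the primary endpoint. The 2.2.1 count is not an SAE rate in the sense of 8.5, and part of it may not be captured. Section 3.1 adds a further composite under the same name. The counts agree on events that meet 8.5 and fall within the composite concerned. Those under 2.2.1 and 8.5 differ for findings below the 8.5 threshold, including those exempt under 8.7.

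The size is unknown. The threefold to sixteenfold range rests wholly on assumed rates, and a reader should not conclude from it that most primary events will be non-serious. With 10 subjects per arm and no stated power, no powered inference is lost. What is lost is a clear meaning for the headline safety result and assurance that it is complete. Because this is the primary endpoint and the correction is cheap, it should be made before the primary analysis.

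**What to change.** 1. Reconcile the TE-SAE definition across 2.2.1, 3.1, 8.5 and 8.7.
2. Report two separate one-month incidences by arm: (a) SAEs meeting 8.5, and (b) clinically significant laboratory results or conditions not meeting 8.5. Do not call the combined count an SAE rate.
3. State that, for post-infusion findings, neither the disease-associated exemption in 8.7 nor the expected-progression exclusion in 8.2 stops a last-limb event from being recorded. The endpoint is then captured the same way in every arm.
4. The pilot gate (3.1) and the DSMB guideline (8.1.5 item 9) both rely on a TE-SAE definition, so any change to 2.2.1 affects them or leaves them inconsistent. The sponsor and DSMB must reconcile them. This review does not say which definition should govern either.

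The cost is protocol wording, one extra table and somewhat more non-serious AEs to record. The SAE headline will also be smaller and less sensitive to laboratory toxicity, so (b) must be shown beside (a).

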2.2.2. Secondary Endpoints (Efficacy)

(Assess at Baseline, Week 2, Month 1, Month 3, and Month 6 following IV allogeneic MSC infusion). Assess EPC-colony forming units (CFUs) 2. Assess circulating inflammatory markers (IL-1, IL-6, TNF α , and CRP) 3. Assess circulating angiogenic factors known to mobilize and recruit EPCs (VEGF, SDF-1 α , and SCF)4. Assess FMD%.

3. STUDY DESIGN

3.1 Description of the Study

A Pilot Phase will be performed to test the safety of dose and volume of cells administered via peripheral intravenous infusion. The first three (3) subjects in-group 1 (UCMSCs) will be treated first and safety will be fully assessed. Only if there is no evidence of treatment emergent SAEs in Group 1, treatment of subjects in Group 3 be undertaken.

The subjects in the high dose (Groups 3 & 4) will not be treated until the subjects in the low dose (Groups 1 & 2) have completed their one-month follow-up assessments and safety measures have been reviewed to confirm that there have been no treatment emergent SAE's. Treatment emergent SAE's, defined as the composite of: death, non-fatal pulmonary embolism, stroke, hospitalization for worsening dyspnea and clinically significant laboratory test abnormalities, prior to proceeding with the treatment of further subjects.

Subjects in each pilot phase group (Group 1, 2, 3 and 4) will not be treated less than 5 days apart.

Subjects in the pilot phase will receive a telephone call 5 days post infusion (+/- 1 day) to review adverse events.

The randomized portion of the study will be conducted after a full review of the safety data from the Pilot Phase by the DSMB.

Following the pilot study (12 subjects), thirty (30) subjects that meet inclusion criteria will be scheduled to undergo peripheral intravenous infusion.

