Three (3) subjects will be treated with a single administration of 2×10^7 (20 million) UCMSCs delivered via peripheral intravenous infusion.

Group 2 (3 subjects)

Three (3) subjects will be treated with a single IV administration of 2×10^7 (20 million) BMMSCs delivered via peripheral intravenous infusion.

The subjects in the high dose (Groups 3 & 4) will not be treated until the subjects in the low dose (Groups 1 & 2) have completed their one-month follow-up assessments and safety measures have been reviewed to confirm that there have been no treatment emergent SAE's.

Group 3 (3 subjects)

Three (3) subjects will be treated with a single IV administration of 1×10^8 (100 million) UCMSCs delivered via peripheral intravenous infusion.

Group 4 (3 subjects)

Three (3) subjects will be treated with a single IV administration of 1×10^8 (100 million) BMMSCs delivered via peripheral intravenous infusion.

Randomized Phase (30 subjects)

Group A (10 subjects – UCMSCs)

Ten (10) subjects will be treated with a single administration of 1×10^8 (100 million) UCMSCs delivered via peripheral intravenous infusion.

Group B (10 subjects – BMMSCs)

Ten (10) subjects will be treated with a single administration of 1×10^8 (100 million) BMMSC delivered via peripheral intravenous infusion.

Group C (10 subjects – Placebo)

Ten (10) subjects will be treated with a single administration of placebo delivered via peripheral intravenous infusion.

Subjects in each pilot phase group (Group 1, 2, 3 and 4) will not be treated less than 5 days apart.

The randomized portion of the study will be conducted after a full review of the safety data from the Pilot Phase by the DSMB

Patients will be randomized in a 1:1:1:1 ratio to one of the 3 groups in the randomized phase. For subjects randomized to B (BMMSCs); the cells will be derived from a healthy allogeneic bone marrow donor (obtained by iliac crest aspiration).

For subjects randomized to Group A (UCMSCs); the cells will be derived from a healthy allogeneic umbilical cord tissue donor.

Route of Administration	Peripheral Intravenous Infusion
Duration of Study Participation	12 months (Follow-up will be at 2 weeks, 1 Month, 3, 6, and 12 months.)
Inclusion Criteria	
1. Provide written informed consent2. Subjects age ≥ 21 and ≤ 95 years at the time of signing the Informed Consent Form.3. Each subject must have endothelial dysfunction. Endothelial dysfunction Criteria:

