8.1.5 Subject Stopping Guidelines

This guideline is to be used to indicate boundaries requiring discussion by the Data and Safety Monitoring Board (DSMB) and is designed to assist the independent DSMB in overseeing the study. The DSMB may also request additional interim analyses and develop other criteria including provision for monitoring of potential late effects to determine when to intervene in the enrollment or treatment of subjects in the study. The first more conservative stopping guideline is to monitor subjects for unexpected SAEs where there is a reasonable possibility that the study product or administration procedure caused the event within 30 days of administration including subject death, grade 3 myocardial infarction, grade 3 hemodynamically unstable ventricular tachycardia or grade 3 LV perforation. Study accrual and further treatment of subjects will be put on hold if any subjects experience one of these events. The DSMB will be notified within 24 hours of the occurrence of these events and will be convened within 3 business days to review the event and study.

The following are subject stopping guidelines:

5. Any subject who develops persistent (that is, still existing more than 3 hours after the end of IP infusion) cardiorespiratory signs or symptoms (for example, shortness of breath, tachypnea, tachycardia, Bradycardia, hypotension, or palpitations) will continue with all scheduled follow-up if such follow-up is considered safe in the opinion of the Investigator.
6. Any subject whose infusion is stopped due to cardiorespiratory distress will receive no further IP infusions but will continue with all scheduled follow-up if such follow-up is considered safe in the opinion of the Investigator.
7. Any subject who develops any sign or symptom that, at the discretion of the Investigator, warrants the discontinuation of infusion will receive no further IP infusions but will continue with all scheduled follow-up if such follow-up is considered safe in the opinion of the Investigator.
8. Infusion of the IP may be stopped if there is an adverse event that the Investigator believes is related to the IP or if there is an issue with the IP infusion.

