9. The proportion of subjects experiencing TE-SAE as defined in Section 2.2.1 will be monitored within 30 days of infusion. This guideline is designed to assist the independent DSMB in overseeing the study and indicate boundaries needing discussion by the DSMB. The DSMB may also request additional interim analyses

and develop other criteria including provision for monitoring of potential late effects to determine when to intervene in the enrollment or treatment of subjects in the study.

10. Monitoring of key safety endpoints (refer to Table 8 in section 2.2.1) will be conducted.
11. The stopping guidelines serve as a mechanism for consultation with the DSMB for additional review, and are not formal “stopping rules” that would mandate automatic closure of study enrollment. It is designed to assist the independent DSMB in overseeing the study. The DSMB may also request additional interim analyses and develop other criteria including provision for monitoring of potential late effects to determine when to intervene in the enrollment or treatment of subjects in the study.
12. Study accrual and further treatment of subjects will be stopped if multiple (i.e. more than 1) subjects develop cardiorespiratory signs and symptoms that are persistent or lead to discontinuation of infusion.

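### Section 3.1 defines TE-SAE at the low-to-high-dose gate more narrowly than the primary endpoint does, so one off-list, non-laboratory event judged unrelated neither bars nor pauses escalation

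*Combined protocol and SAP*

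**What the plan says.** Section 2.2.1 makes TE-SAE within one month of infusion the primary endpoint and defines it by seriousness criteria. An event counts if it "is life-threatening event (e.g., stroke or non-fatal pulmonary embolism"), or if it "requires inpatient hospitalization or prolongation of existing hospitalization (e.g., for worsening dyspnea); results in persistent or significant disability/incapacity", or if it results in death, "or leads to clinically significant untoward laboratory test result(s) or medical condition(s"), the last by investigator judgment.

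Section 3.1 uses the same term to control the step from 20 million to 100 million cells. It first says "Only if there is no evidence of treatment emergent SAEs in Group 1, treatment of subjects in Group 3 be undertaken". It then holds both high-dose groups until both low-dose groups have finished one-month follow-up and "safety measures have been reviewed to confirm that there have been no treatment emergent SAE's". The definition attached there is "Treatment emergent SAE's, defined as the composite of: death, non-fatal pulmonary embolism, stroke, hospitalization for worsening dyspnea and clinically significant laboratory test abnormalities".

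The Protocol Synopsis states the same gate without a definition. Section 8.1.5, item 9, uses the wider one: "The proportion of subjects experiencing TE-SAE as defined in Section 2.2.1 will be monitored within 30 days of infusion".

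**The concern.** In 2.2.1, embolism, stroke and worsening dyspnea illustrate a wider class. In 3.1 they have become the class itself, with nothing to signal that the list is open. Because 3.1 is the only text that defines the term at the gate, a team following it literally would check five items and proceed.

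The gate rests on six subjects, three per product, and precedes a fivefold increase in dose. If its definition is narrower than the primary endpoint's, a low-dose subject can have an event that counts in the primary analysis and the gate still passes. An inpatient admission for something other than dyspnea, or a lasting disability, would be such an event unless another rule catches it. The check therefore has to cover every other rule that could make escalation wait.

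**Working it through.** The plan states no operating characteristic for this gate, and Section 9.1 says the sample size had no formal statistical justification, so there is no figure to reproduce. The check is a comparison of texts.

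**Step 1: the two definitions, limb by limb**

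| Section 2.2.1 limb | Section 3.1 list |
|---|---|
| Death | Covered |
| Life-threatening event, any cause | Only embolism and stroke |
| Hospitalization or its prolongation, any cause | Only admission for worsening dyspnea |
| Persistent or significant disability | Absent |
| Clinically significant laboratory result or medical condition | Laboratory results only |

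One limb is fully covered, three are partly covered and one is absent (1 + 3 + 1 = 5).

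**Step 2: subjects and dose at the gate.** Groups 1 and 2 give 3 + 3 = 6 subjects. The dose ratio is 100 million / 20 million = 5.

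**Step 3: would any other rule make escalation wait for a single off-list event?**

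- *Section 8.1.5, opening hold.* It applies to "unexpected SAEs where there is a reasonable possibility that the study product or administration procedure caused the event within 30 days of administration", pauses treatment and convenes the DSMB within 3 business days. Section 8.14 treats every AE as unexpected, so causality decides. The sentence goes on to name particular events. I read those as examples, which gives the hold its widest reach; as a closed list it would catch less. Possibly related events are held. Events judged unrelated are not.
- *Section 3.1, laboratory item.* It carries no seriousness threshold, so an off-list event with a clinically significant laboratory abnormality would probably trip the gate.
- *Section 8.1.5, item 9.* It uses the 2.2.1 definition but states no boundary and no hold.
- *Section 8.1.5, item 12.* It stops treatment whatever the cause, but needs more than one subject with persistent or infusion-ending cardiorespiratory signs.
- *Section 9.3.* The DSMB Chair is told of each SAE. Nothing waits on that notice.
- *Section 9.4.3.2.* Monthly safety reports are available to the DSMB. Nothing waits on these either.
- *Section 9.4.3.3.* The full DSMB review follows treatment and 30 days of follow-up of all pilot subjects, so it comes after Groups 3 and 4 have been treated.

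**Step 4: what is left.** An event that is off the 3.1 list, has no clinically significant laboratory abnormality, is judged unrelated, and occurs within a month in one of six subjects.

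**Step 5: can it be sized?** Only by assumption. Let p be the per-subject chance of an off-list, non-laboratory event and h the share caught by the 8.1.5 hold. Then r = p(1 − h), and the chance of at least one uncaught event in six subjects is 1 − (1 − r)^6.

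- p = 0.02, h = 0.90: r = 0.002, and 1 − 0.998^6 = 1.2%.
- p = 0.05, h = 0.50: r = 0.025, and 1 − 0.975^6 = 14.1%.

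Neither p nor h comes from the documents. A different set of assumptions, which ignores the hold, takes p as the rate of any 2.2.1 event (0.05 to 0.30) and f as the share on the list (0.25 to 0.75). The chance that the list passes when 2.2.1 would not is (1 − pf)^6 − (1 − p)^6, which runs from 6% to 51%. The spread reflects the assumptions, so no rate is carried into the conclusion.

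**The case against.** The best case for the plan is that little escapes in practice. Section 3.1 also requires a full safety assessment of Group 1 and a review of safety measures, which is more than a checklist. The list sits in an incomplete sentence, and the synopsis and item 9 point the other way, so this looks like loose drafting. Section 8.12 has SAEs recorded within 24 to 48 hours, well inside the one-month wait. The DSMB may set further criteria (8.1.5) and call an unscheduled meeting (9.4.4.3). Letting escalation proceed after a plainly unrelated admission is also defensible. The DSMB Charter, and the Table 8 that the plan places in 2.2.1, are not in the text available and might say more.

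Most of this stands and limits the severity. It does not remove the mismatch: each of these routes allows a pause, and none requires one.

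Four stronger readings are tempting and are not supported:

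- *Any off-list serious event slips through.* It does not; the 8.1.5 hold covers possibly related ones.
- *A cardiac event, such as syncope in a patient with heart disease, would be called unrelated and so escape.* Section 8.10 lets the investigator weigh underlying disease, but its Possible category allows for a competing cause, so the event may well fall under the hold. Section 4.2 also excludes advanced or recent cardiac disease.
- *On-list events go to the DSMB while off-list ones do not.* Section 3.1 sends nothing to the DSMB; an on-list event simply bars escalation.
- *The gate was narrowed on purpose.* Nothing in the documents says so.

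**Conclusion.** The plan is wrong as written on this point: it gives one term two definitions, and the narrower one governs dose escalation. Confidence in the mismatch is high, because it rests only on the text. The consequence is limited to the residual case in Step 4, and its frequency cannot be derived from the documents. That limit assumes the wide reading of the 8.1.5 hold and a literal reading of the laboratory item.

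A second defect pulls the other way. An on-list event, even one that proves unrelated, closes the route to the high dose, with nobody named to review it and no step that could reopen it.

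Severity is minor to moderate. It warrants correction because the rule protects subjects and the correction is cheap. It does not undermine the design.

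**What to change.** In Section 3.1, replace the five-item list with a reference to the TE-SAE definition in Section 2.2.1, and add the same reference to the gate in the synopsis.

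State that the planned overnight stay with next-day discharge (Appendix 1) is not a hospitalization for this purpose, while an added admission or a delayed discharge is. Without this, the wider hospitalization limb could be read as met by every subject.

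Add to both places: *If any TE-SAE occurs in Groups 1–2, Groups 3–4 are not treated until the DSMB has reviewed the event and recommended proceeding.* Reword the sentence in 3.1 that allows Group 3 only after a clean Group 1 so that it agrees. This supplies both the reviewer and the release step. Leave the 8.1.5 hold as a separate rule.

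The cost is wording in 3.1 and the synopsis, with no new data or subjects. The downside is an occasional pause for an event that proves unrelated, kept short if the 3-business-day timetable in 8.1.5 is adopted. The wider definition also brings in medical conditions identified by investigator judgment, with no stated threshold, so some discretion remains and some pauses will be for minor matters. How often cannot be estimated from the documents.
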